If a tumor assessment shows disease progression, it should be confirmed pathologically and/or by unequivocal radiographic evidence from the scan. If the scan shows equivocal findings (e.g., mediastinal nodes measure < 1.5 cm in the short axis, lung parenchymal lesions or visceral lesions measuring < 1 cm in the longest diameter), a biopsy should be performed. If a biopsy is not feasible or safe, then confirmatory scans should be performed no later than the next scheduled assessment, or earlier if clinically indicated. If a biopsy for disease progression confirmation is performed, any leftover biopsy tissue is strongly encouraged to be submitted for exploratory biomarker research (optional consent required for exploratory research; see Section 4.5.8 for details). The biopsy should be performed prior to starting the next anti-cancer therapy. If the biopsy does not show evidence of disease progression (e.g., non-malignant infiltrates), then the patient may continue with scheduled study treatment, assessments, and/or follow-up. After patients who are assessed with confirmed radiographic disease progression per RECIST v1.1 and have discontinued or completed study treatment, they will continue to undergo tumor assessments according to local standard of care.

Response will be assessed according to RECIST v1.1 (see [Appendix 4](#)). Objective response at a single timepoint will be determined by the investigator according to RECIST v1.1.

Patients will be asked to complete PRO questionnaires every other cycle starting on Day 1 of Cycle 1, at treatment discontinuation/completion, at scheduled tumor assessments after treatment is discontinued for any other reason than radiographic disease progression, and post-treatment follow-up at 3 and 6 months (± 30 days) following radiographic disease progression (see Section 4.5.10 and [Appendix 1](#)).

During the study, serum samples will be collected to monitor tiragolumab and atezolizumab pharmacokinetics and to detect the presence of antibodies to tiragolumab and atezolizumab. Patient samples, including archival and fresh tumor tissue, serum, plasma, and blood samples, will also be collected for exploratory biomarker assessments.

Safety assessments will include the incidence, nature, and severity of adverse events, protocol-mandated vital signs, laboratory abnormalities, and other protocol-specified tests that are deemed critical to the safety evaluation of the study.

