3.1.2 Treatment after Disease Progression

During the study, patients who meet criteria for disease progression per RECIST v1.1 and show evidence of clinical benefit may continue study treatment for up to 13 cycles of treatment, at the investigator's discretion, provided that the patient meets all of the following criteria:

- Evidence of clinical benefit, as assessed by the investigator
- Absence of metastatic disease
- Absence of symptoms and signs (including worsening of laboratory values (e.g., new or worsening hypercalcemia) indicating unequivocal progression of disease

- No decline in ECOG Performance Status that can be attributed to disease progression

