Patients will undergo tumor assessments at screening and every 8 weeks (± 7 days) for 48 weeks following Day 1 of Cycle 1 regardless of treatment delays (see [Appendix 1](#)). After the completion of the Week 48 tumor assessment, tumor assessment will be required every 12 weeks (± 7 days) regardless of treatment delays until confirmed radiographic disease progression (as defined by growth of existing lesions, new lesions, or recurrence of previously resolved lesions) per RECIST v1.1, withdrawal of consent, or study termination by the Sponsor, whichever occurs first (see [Appendix 1](#)). Patients who are treated beyond disease progression per RECIST v1.1 will undergo tumor assessments at the frequency described above until study treatment is discontinued. At the investigator's discretion, scans may be performed at any time if progressive disease or loss of clinical benefit is suspected.

Patients who discontinue treatment for reasons other than radiographic disease progression per RECIST v1.1 (e.g., toxicity, symptomatic deterioration, completion of study treatment) will continue scheduled tumor assessments at the frequency described above until confirmed radiographic disease progression per RECIST v1.1, withdrawal of consent, death, or study termination by the Sponsor, whichever occurs first. Patients who start a new anti-cancer therapy, in the absence of confirmed radiographic disease progression per RECIST v1.1, will also continue tumor assessments at the frequency described above until radiographic disease progression per RECIST v1.1, withdrawal of consent, death, or study termination by the Sponsor, whichever occurs first.

If a tumor assessment shows radiographic disease progression per RECIST v1.1, and a subsequent scan confirms radiographic disease progression per RECIST v1.1, the date of disease progression is the date of the first assessment of progression.

Response will be assessed by the investigator on the imaging modalities detailed above, using RECIST v1.1 (see [Appendix 4](#)). The investigator's assessment of overall tumor response at all timepoints should only be based on RECIST v1.1. Assessments should be performed by the same evaluator if possible to ensure internal consistency across visits. Results must be reviewed by the investigator before dosing at the next cycle.

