Patient-reported outcomes (EORTC QLQ-C30, EORTC QLQ-LC13, EORTC IL46, and EQ-5D-5L) will be collected on Day 1 of Cycle 1 (baseline) prior to administration of study drug, and at every other study treatment cycle prior to the administration of study drug (i.e., on Day 1 of Cycles 3, 5, 7, etc.) until radiographic disease progression per RECIST v1.1, and at the study treatment discontinuation/completion visit. Patients who discontinue study treatment for any reason other than radiographic disease progression per RECIST v1.1 (e.g., toxicity, symptomatic deterioration) will complete PROs at each tumor assessment visit until radiographic disease progression per RECIST v1.1, withdrawal of consent, death, or study termination by the Sponsor, whichever occurs first.

During the post-treatment follow-up, PROs will be completed 3 months (\pm 30 days) and 6 months (\pm 30 days) following radiographic disease progression per RECIST v1.1 (or loss of clinical benefit for patients who continue study treatment after disease progression per RECIST v1.1). The PROs at 3 and 6 months after disease progression or after treatment discontinuation/completion visit may be collected by telephone.

Patients whose native language is not available with the questionnaires are exempted from completing all PRO assessments.

The Sponsor will not derive adverse events reports from PRO data (see Section 5.3.5.13).

4.5.10.2 Description of Clinical Outcome Assessment Instruments EORTC QLQ-C30, EORTC QLQ-LC13 and EORTC IL46

The EORTC QLQ-C30 is a validated, reliable self-reported measure (Aaronson et al. 1993; Fitzsimmons et al. 1999) (see [Appendix 5](#)). It consists of 30 questions that assess five aspects of patient functioning (physical, emotional, role, cognitive, and social), three symptom scales (fatigue, nausea and vomiting, and pain), GHS and QoL, and six single items (dyspnea, insomnia, appetite loss, constipation, diarrhea, and financial difficulties) with a recall period of the previous week. Scale scores can be obtained for the multi-item scales. The functioning and symptoms items are scored on a 4-point scale that ranges from "not at all" to "very much," and the GHS and QoL items are scored on a 7-point scale that ranges from "very poor" to "excellent." The EORTC QLQ-C30 module takes approximately 15 minutes to complete.

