Key Secondary Objectives (continued)	Estimand Definition (continued)
To evaluate the efficacy of tiragolumab plus atezolizumab compared with durvalumab in the PPAS	DOR, as assessed by the investigator. The estimand is defined in the same way as for IRF-assessed DOR, except that DOR is determined by the investigator.
To evaluate the quality of life of patients treated with tiragolumab plus atezolizumab compared with durvalumab in the PPAS	
TTCD, with the estimand defined similarly as for the primary endpoints in terms of population and treatments; the other attributes are defined as follows:
 
 
Endpoint: the time from the date of randomization until the first confirmed clinically meaningful deterioration on each respective score. 
Confirmed clinically meaningful deterioration in symptoms using the EORTC QLQ-LC13 is defined as a clinically meaningful increase from baseline in a symptom score that must be held for at least two consecutive assessments or an initial clinically meaningful increase from baseline followed by death from progressive disease. Confirmed clinically meaningful deterioration in GHS and physical functioning using EORTC QLQ-C30 is defined as a clinically meaningful decrease from baseline in GHS or physical functioning scale score that must be held for at least two consecutive assessments or an initial clinically meaningful decrease above baseline followed by death due to progressive disease.
 
 
Intercurrent events and handling strategies: 
 
Early discontinuation from study treatment from any cause prior to the respective event of interest: treatment policy strategy
 
Start of non-protocol anti-cancer therapy prior to the respective event of interest: treatment policy strategy
 
Death that occurs before patients report any clinically meaningful deterioration: treatment policy strategy
 
 
 
Population-level summary: hazard ratio for TTCD
 

To evaluate the efficacy of tiragolumab plus atezolizumab compared with durvalumab in the FAS	The estimands for the efficacy objectives in the FAS are defined in the same way as for the PPAS.
To evaluate the quality of life of patients treated with tiragolumab plus atezolizumab compared with durvalumab in the FAS	The estimand for TTCD in the FAS is defined in the same way as for the PPAS.

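### Section 4.5.10.1 stops on-treatment PROs at RECIST progression even when study treatment continues, which leaves gaps in time to confirmed deterioration, and its 3- and 6-month follow-up anchor differs from Section 3.1.1

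*Protocol*

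**What the plan says.** Protocol Section 4.5.10.1 schedules PROs at baseline and then "at every other study treatment cycle prior to the administration of study drug", that is, on Day 1 of the odd-numbered cycles. This runs "until radiographic disease progression per RECIST v1.1, and at the study treatment discontinuation/completion visit". The 3- and 6-month follow-up PROs are counted from radiographic progression, "or loss of clinical benefit for patients who continue study treatment after disease progression per RECIST v1.1". A later sentence on telephone collection words the anchor a third way, as progression or the discontinuation/completion visit.

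Protocol Section 3.1.1 says: "Patients will be asked to complete PRO questionnaires every other cycle starting on Day 1 of Cycle 1, at treatment discontinuation/completion". It gives no stop at progression for the on-treatment PROs. It counts the 3- and 6-month PROs from radiographic progression, with no alternative for patients still on treatment.

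Under Section 3.1.2, patients who progress per RECIST v1.1 but meet all the listed criteria "may continue study treatment for up to 13 cycles of treatment". Section 3.3, in contrast, lists RECIST progression among the events that end treatment.

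TTCD is a key secondary endpoint in SAP Table 1. Early treatment discontinuation and new anti-cancer therapy are both handled by treatment policy. A deterioration "must be held for at least two consecutive assessments", or be an initial deterioration followed by death. Protocol Section 6.5.2.8 and SAP Section 4.3.1.5 censor event-free patients at their last completed assessment, not at progression.

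**The concern.** The endpoint and the collection schedule do not match. TTCD follows the patient through progression, but for a patient treated past progression the schedule in 4.5.10.1 falls silent there. The rule is also uneven. A patient who is off treatment at progression has PROs due 3 and 6 months later; a patient who stays on study drug has none due until treatment ends.

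Deterioration that begins in the gap cannot be recorded when it happens. It may be seen late, at the discontinuation/completion visit, or not at all if it has resolved by then. Protocol Section 3.4.11 justifies the PROs as showing how delay in radiographic progression relates to delay in symptoms, and that needs data on both sides of progression.

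The differing anchors add a practical problem: for a patient treated past progression, a site cannot apply 3.1.1 and 4.5.10.1 together.

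**Working it through.** The documents give no figure for this gap, so the check is schedule arithmetic.

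**Inputs.** Cycles last 28 days, with at most 13 (Protocol 3.1.1). PROs fall on Day 1 of odd cycles (4.5.10.1). Scans are every 8 weeks, so the first is at Week 8 (4.5.6). The discontinuation/completion visit is at most 30 days after the final dose (4.6.1).

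**PRO weeks.** Cycle k Day 1 falls at week 4(k − 1). Cycles 1, 3, 5, 7, 9, 11 and 13 give Weeks 0, 8, 16, 24, 32, 40 and 48, which is 7 on-treatment PROs.

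**Next PRO after the stop.** The final dose is at Week 48. The completion visit lies between Week 48 and Week 48 + 30/7 = 52.3.

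**Gap.** For progression at week t, with no delays and all 13 cycles given, the gap runs from 48 − t to 52.3 − t weeks. A PRO due in the same week as the scan is taken as collected.

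| Progression (week) | On-treatment PROs lost | Gap (weeks) |
|---|---|---|
| 8 | 5 (Weeks 16, 24, 32, 40, 48) | 40 to 44.3 |
| 16 | 4 | 32 to 36.3 |
| 24 | 3 | 24 to 28.3 |
| 40 | 1 | 8 to 12.3 |

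Section 4.5.10.1 does not say whether the stop applies at first or at confirmed progression. If a site waits for confirmation at Week 16, the Week 16 row applies. Week 8 is not a strict maximum: a scan at Week 7, inside the ±7-day window, could also remove the Cycle 3 PRO, and delays after progression lengthen the gap.

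**Anchors, for progression at Week 8.** Under 3.1.1 the 3-month PRO falls at 8 + 3 × 30.44/7 = Week 21 and the 6-month PRO at 8 + 6 × 30.44/7 = Week 34, each ± 30 days. Under 4.5.10.1 neither is due while clinical benefit continues. The choice of anchor therefore decides whether the gap is broken twice or not at all.

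**Effect on TTCD in the Week 8 case.** If the Week 8 score is the first deteriorated one, the next scheduled score that could confirm it comes 40 to 44 weeks later. If deterioration starts at Week 20 (an illustration), it is first recorded 48 − 20 = 28 to 52.3 − 20 = 32.3 weeks after onset, and still needs confirmation. The route of one deteriorated score followed by death also requires that score to have been collected.

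**The case against.** Section 3.1.1 is an overview sentence that refers the reader to Section 4.5.10 and Appendix 1. It omits the stop at progression; it does not deny it. A reader might infer an outright contradiction on the stop, but the text supports only an unreconciled difference. The visible conflict is in the 3- and 6-month anchor.

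The subgroup is selected. Section 3.1.2 requires clinical benefit, no metastatic disease, no symptoms or signs of unequivocal progression, and no decline in performance status attributable to progression. Loss of clinical benefit ends treatment under Section 4.6.1 and brings a PRO within 30 days of the final dose. So a reader should not infer that TTCD goes unmeasured, or that the gap falls where deterioration is most likely. Measurement becomes sparse and then resumes. Under Section 3.3, treatment would end at progression and the gap would not arise. Footnote bb in Appendix 1 might also state a single rule.

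These points reduce the number of patients affected and make 44 weeks an extreme case. They do not remove the stop in 4.5.10.1. An investigator's judgement of clinical benefit is not the same as a stable score, and TTCD counts a change of 10 points or more whether or not it is attributed to progression. Whatever footnote bb says, the body sections still differ on the anchor.

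**Conclusion.** The point holds in a limited form. As written, 4.5.10.1 drops on-treatment PROs after RECIST progression for patients who remain on study drug, and TTCD needs those data. The loss reaches 5 of 7 on-treatment PROs and 40 to 44 weeks for progression at Week 8. It is 3 PROs and about 24 to 28 weeks for progression at Week 24. Both figures assume that all 13 cycles are given without delay and that the criteria in 3.1.2 stay met throughout.

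The number of such patients is not given. Both arms may be treated past progression (3.4.10), and nothing visible shows how often this would occur in either, so the size and direction of any effect on the TTCD hazard ratio are unknown. A claim that one arm is favoured is not supported.

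A reader might also infer that toxicity holds delay PROs, because tumor assessments run "following Day 1 of Cycle 1 regardless of treatment delays" and the PRO text has no such wording. That inference is not supported either. No visible passage says PROs are skipped during a hold, part of the interruption rules in 5.1.5.2 is redacted, and footnote bb is not visible.

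**What to change.** In Section 4.5.10.1, replace the stop at RECIST progression with collection on Day 1 of every other cycle for as long as study treatment continues, including past progression. State one anchor for the 3- and 6-month PROs and use it in 3.1.1, 4.5.10.1 and Appendix 1. Sections 3.1.2 and 3.3 on treatment after progression must also be reconciled; which of them is right is not a matter for this point.

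Tying PROs to Day 1 treatment visits is simpler than using the tumor-assessment calendar, which becomes 12-weekly after Week 48. It also avoids relying on the telephone, which 4.5.10.1 allows during treatment only in limited circumstances. In the Week 8 case without delays, the fix restores the 5 lost PROs and brings the longest planned interval down to 8 weeks.

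The cost is a wording change, a notice to sites and a few extra questionnaires at visits that already take place. From the protocol's own times, each set takes 15 + 7 + 3 = 25 minutes, plus one IL46 item with no stated time. That is at most 5 × 25 = 125 minutes for the Week 8 patient.

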4.5.12 Mandatory Biopsy at Disease Progression

Patients in both treatment arms will undergo a mandatory tumor biopsy to obtain a tumor sample, if clinically feasible, at the time of radiographic disease progression or prior to the start of the next anti-cancer treatment whichever is sooner. Acceptable samples include core-needle biopsies for deep tumor tissue (minimum three cores, if clinically feasible) or excisional, incisional, punch, or forceps biopsies for cutaneous, subcutaneous, or mucosal lesions.

4.5.13 Optional Tumor Biopsies

Consenting patients will undergo optional tumor biopsies at the investigator's discretion at any time (if deemed clinically feasible by the investigator). It is preferable that optional tumor biopsies be collected at the first evidence of radiographic response, or at the first evidence of radiographic disease progression during treatment (within 40 days of

radiographic progression or at the start of the next anti-cancer treatment, whichever is sooner). Samples collected by means of resection, core-needle biopsy (at least three cores, if clinically feasible), or excisional, incisional, punch, or forceps biopsy are preferred.

The Informed Consent Form will contain a separate section that addresses optional biopsies. A separate, specific signature will be required to document a patient's agreement to undergo optional biopsies. The investigator should document whether or not the patient has given consent to participate and (if applicable) the date(s) of consent, by signing the Optional Biopsy Sample Informed Consent Form.

Samples may be used for exploratory biomarker research as described in Section 4.5.14. For sampling procedures, storage conditions, and shipment instructions, see the laboratory manual. Refer to Section 4.5.14.3 for details on duration of sample storage, use of samples after patient withdrawal, confidentiality standards for data, and availability of data from biomarker analyses.

4.5.14 Optional Samples for Research Biosample Repository

4.5.14.1 Overview of the Research Biosample Repository

The Research Biosample Repository (RBR) is a centrally administered group of facilities used for the long-term storage of human biological specimens, including body fluids, solid tissues, and derivatives thereof (e.g., DNA, RNA, proteins, and peptides).

The collection, storage, and analysis of RBR samples will facilitate the rational design of new pharmaceutical agents and the development of diagnostic tests, which may allow for individualized drug therapy for patients in the future.

Samples for the RBR will be collected from patients who give specific consent to participate in this optional research. Research Biosample Repository samples will be analyzed to achieve one or more of the following objectives:

- To study the association of biomarkers with efficacy or disease progression
- To identify safety biomarkers that are associated with susceptibility to developing adverse events or can lead to improved adverse event monitoring or investigation
- To increase knowledge and understanding of disease biology and drug safety
- To study drug response, including drug effects and the processes of drug absorption and disposition
- To develop biomarker or diagnostic assays and establish the performance characteristics of these assays

4.5.14.2 Approval by the Institutional Review Board or Ethics Committee

[figure not shown]
Collection, storage, and analysis of RBR samples is contingent upon the review and approval of the exploratory research and the RBR portion of the Informed Consent Form by each site's IRB/EC and, if applicable, an appropriate regulatory body. If a site has not

been granted approval for RBR sampling, this section of the protocol (Section 4.5.14) will not be applicable at that site.

4.5.14.3 Sample Collection

The following samples will be stored in the RBR and used for research purposes, including, but not limited to, research on biomarkers related to tiragolumab, atezolizumab, NSCLC, or drug safety:

- Leftover blood, serum, plasma, and tumor tissue samples (with the exception of remaining archival tissue blocks, which will be returned to sites) and any derivatives thereof (e.g., DNA, RNA, proteins, and peptides), including leftover tissue samples from medically indicated procedures (e.g., bronchoscopy, esophagogastroduodenoscopy, colonoscopy) performed at the investigator's discretion during the study

Data generated from RBR samples will be analyzed in the context of this study but may also be explored in aggregate with data from other studies. The availability of a larger dataset will assist in identification and characterization of important biomarkers and pathways to support future drug development.

For sampling procedures, storage conditions, and shipment instructions, see the laboratory manual.

Research Biosample Repository samples are to be stored until they are no longer needed or until they are exhausted. However, the RBR storage period will be in accordance with the IRB/EC-approved Informed Consent Form and applicable laws (e.g., health authority requirements).

4.5.14.4 Confidentiality

Research Biosample Repository samples and associated data will be labeled with a unique patient identification number.

Patient medical information associated with RBR samples is confidential and may be disclosed to third parties only as permitted by the Informed Consent Form (or separate authorization for use and disclosure of personal health information) signed by the patient, unless permitted or required by law.

Given the complexity and exploratory nature of the analyses of RBR samples, data derived from these analyses will generally not be provided to study investigators or patients unless required by law. The aggregate results of any conducted research will be available in accordance with the effective Sponsor policy on study data publication.

Data generated from RBR samples must be available for inspection upon request by representatives of national and local health authorities, and Sponsor monitors, representatives, and collaborators, as appropriate.

Any inventions and resulting patents, improvements, and/or know-how originating from the use of the RBR data will become and remain the exclusive and unburdened property of the Sponsor, except where agreed otherwise.

